16 SIGNATURE PAGE
17 REFERENCES
APPENDIX 1: TRIAL STEERING COMMITTEE TERMS OF REFERENCE
THE ROLE OF THE LIFT TSC
LIFT TSC MEMBERSHIP

LIST OF ABBREVIATIONS

[figure not shown]
AE	Adverse Event	
BTC	Bristol Trials Centre	
CI	Chief Investigator	
CONSORT	Consolidated Standards of Reporting Trials	
CRF	Case Report Form	
CRN	Clinical Research Network	
CSO	Clinical Study Officer	
DMC	Data Monitoring Committee	
EU	European Union	
GDPR	General Data Protection Regulation	
GP	General Practitioner	
HRA	Health Research Authority	
IAPT	Improving Access to Psychological Therapies	
GCP	Good Clinical Practice	
ISF	Investigator Site File	
ISRCTN	International Standard Randomised Controlled Trials Number	
ІТТ	Intention-to-treat	
NHS	National Health Service	
NHS R&D/R&I	National Health Service Research & Development/Research & Innovation	
NICE	National Institute for Health and Care Excellence	
NIHR CRN	National Institute for Health Research Clinical Research Network	
NIHR HTA	National Institute for Health Research Health Technology Assessment	
PI	Principal Investigator	
PICs	Patient Identification Centres	
PIL	Participant Information Leaflet	
PPE	Personal Protective Equipment	
PPI	Patient and Public Involvement	
PROM	Patient reported outcome measure	
QALY	Quality Adjusted Life Years	
RCT	Randomised Controlled Trial	
R&D	Research and Development	
REC	Research Ethics Committee	
SAE	Serious Adverse Event	
SAP	Statistical Analysis Plan	
SD	Standard Deviation	
SLA	Service Level Agreement	
SOP	Standard Operating Procedure	
SQL	Structured Query Language	
TAU	Treatment As Usual	
TMF	Trial Master File	
TMG	Trial Management Group	
TSC	Trial Steering Committee	
UK	United Kingdom	
UKCRC	UK Clinical Research Collaboration	

TRIAL SUMMARY

Trial title	Promoting good health in Care Leavers (CLs) through training for Personal Advisors (PAs)		
Short title	Life In Transition: Improving Health Outcomes for Care Leavers		
Acronym	LIFT		
Chief Investigator	[name]		
Sponsor	University of Bristol		
Funder	National Institute for Health Research (NIHR)		
Trial design	Cluster-randomised feasibility trial		
Planned sample size	6 clusters (teams of Personal Advisors); circa 30 Personal Advisors; 60 care leavers		
Inclusion criteria	 Care Leavers i) Aged over 16 years at baseline ii) Allocated to the Leaving Care team for the first time, in a four-month period beginning 2 months prior to baseline data collection iii) Not simultaneously on the caseload of a social worker. 		
Exclusion	 Care Leavers living in foster care (other than 'Staying Put' foster care) or in a residential or secure setting of any kind, including custody, remand, or hospital; or they are simultaneously allocated to the caseload of a qualified social worker (for example, as a result of being a parent themselves); or deemed by the local authority to present a risk to themselves or to research staff. 		
criteria	 living in foster care (other than 'Sta secure setting of any kind, includir they are simultaneously allocated example, as a result of being a particular setting of being a particular setting and the set of being a particular setting setting a setting s	ng custody, remand, or hospital; or to the caseload of a qualified social worker (for rent themselves); or	
criteria Number of study centres	 living in foster care (other than 'Sta secure setting of any kind, includir they are simultaneously allocated example, as a result of being a particular setting of being a particular setting and the set of being a particular setting setting a setting s	ng custody, remand, or hospital; or to the caseload of a qualified social worker (for rent themselves); or	
Number of study centres	 living in foster care (other than 'Sta secure setting of any kind, includir they are simultaneously allocated example, as a result of being a part deemed by the local authority to part 	ng custody, remand, or hospital; or to the caseload of a qualified social worker (for rent themselves); or resent a risk to themselves or to research staff.	
Number of study centres Treatment	 living in foster care (other than 'Sta secure setting of any kind, includin they are simultaneously allocated example, as a result of being a part deemed by the local authority to part 3 	ng custody, remand, or hospital; or to the caseload of a qualified social worker (for rent themselves); or resent a risk to themselves or to research staff.	
Number of study centres Treatment duration Primary	 living in foster care (other than 'Stasecure setting of any kind, includir they are simultaneously allocated example, as a result of being a pare deemed by the local authority to para 3 3 Training intervention delivered over a three Objectives Feasibility of Study Design	e-month period Outcome Measures The recruitment and retention rates of personal advisors and care leavers, the completion of training by personal advisors in the intervention group, the proportion of care leavers and personal advisors who complete the study assessments, the ability to blind outcome assessors and the potential floor/ceiling effects in our proposed outcomes measures at baseline, post training (for intervention.	
Number of study centres Treatment duration Primary Primary Secondary (Intervention	 living in foster care (other than 'Stasecure setting of any kind, includin they are simultaneously allocated example, as a result of being a pail deemed by the local authority to pail Training intervention delivered over a three Objectives 	e-month period	
Number of study centres Treatment duration Primary Secondary	 living in foster care (other than 'Stasecure setting of any kind, includir they are simultaneously allocated example, as a result of being a pare deemed by the local authority to p 3 Training intervention delivered over a three Objectives Feasibility of Study Design i) Impact on Care Leavers' Health and	e-month period Outcome Measures The recruitment and retention rates of personal advisors and care leavers, the completion of training by personal advisors in the intervention group, the proportion of care leavers and personal advisors who complete the study assessments, the ability to blind outcome assessors and the potential floor/ceiling effects in our proposed outcomes measures at baseline, post training (for intervention.	

	c) Quality of Life	ReQoL20 OR eQoL10 OR EQ-5D-5L
	d) Confidence in health	Revised Perceived Efficacy in Patient-
	professionals	Physician Interactions Questionnaire (PEPPI- 10)
	e) Perceptions of physician empathy	 Questions regarding Care Leavers' Perceptions of Physician Empathy
	f) Psychological coping (Mastery)	Pearlin Mastery Scale
	ii) Cost-effectiveness	
	a. Health Service Usage	Health Service Use Questionnaire
	b. Quality of Life	ReQoL20 OR eQoL10 OR EQ-5D-5L
	iii) Increased knowledge, skills and confidence of Personal Advisors	Online survey
		Individual interview
Study duration	24 months	·

TRIAL FLOW CHART

Analysis

Figure 1 Trial flowchart

1 BACKGROUND AND RATIONALE

1.1 Children looked after and inequalities in health

The number of children being looked after by local authorities has increased year-on-year since 2009. In March 2017 there were 72,670 children looked after in England, of whom 50,470 were in care under a care order, and of whom 4,560 were unaccompanied asylum-seeking children. Looked after and formerly looked after children experience significant health disadvantage during and after their time in care. In 2016, the Care Quality Commission reported that 'support for care leavers was unacceptably poor, with health services failing to cater for their needs or help to prepare them for the next stage in their life ...[with most lacking] adequate health support as they left the care system'.(1 p.36) Inequalities in health amongst looked after children and young people (LACYP) encompass their physical health, sexual and reproductive health, and mental health and wellbeing.

Compared with those living at home, looked after children and young people (LACYP) often have poorer physical and mental health.(2-7) Despite recent improvements (and recognising the difficulties in comparisons with the general population(8)) they remain less likely to have received all routine immunizations,(8, 9) with lowest rates amongst older LACYP and unaccompanied asylum-seeking children.(10, 11) In 2003 Meltzer et al. reported that two thirds of LACYP had at least one physical complaint.(12) The number of LACYP with disabilities is unknown, but ongoing work by [name] finds higher numbers than in the general population.

Compared with those in the general population, LACYP and those leaving care, are at greater risk of early sexual initiation(13) and of sexual exploitation.(14) Barnardo's estimates that one third of those children who experience sexual exploitation are looked-after children. Compared with children living with their families, female LACYP are more likely to become pregnant and LACYP are more likely to become parents at an early age.(15-18) Care experienced young women are more likely to smoke during pregnancy, to have symptoms of depression and deliver a low birthweight baby.(19) They may be at increased risk for pre-term birth(20, 21) and are more likely to have an elevated risk of their own children being taken into care,(22) with a significant number experiencing 'recurrent care proceedings.(23)

Many LACYP enter care with existing mental health problems, often associated with trauma.(24-26) The Departments of Education and Health estimate that almost a half of LACYP have a diagnosable mental health disorder.(27) In a study comparing LAC to children who were otherwise deprived in Britain, Ford et al found that looked-after status was an independent correlate of psychiatric disorders (other than autistic spectrum disorders and generalized anxiety disorder) after adjusting for potential confounders.(25) In a study of the files of 274 UK care leavers, Smith found that, in the opinion of their PAs, 46% had mental health needs, of whom 65% were not receiving any statutory service.(28) Because they are especially prone to isolation and loneliness, CLs may be less likely to seek help, and instead resort to ways of coping that cause further harm e.g. self-harm, drug and alcohol misuse.

The National Service Framework for Children, Young People and Maternity Services recognised LACYP as a particularly vulnerable group.(29) Various policy initiatives have sought to improve their physical, sexual and mental health. The introduction of the LAC named nurse represented a significant investment in promoting the health of children whilst in care, but that responsibility ceases when young people leave care.

1.2 Care leavers

Every year, some 10,000 children aged 16-18 years leave local authority (LA) care in England(18) and many start to lead independent lives. Most make these transitions against a background of significant adversity and trauma, having been removed from the care of their parents due to abuse and neglect.(30, 31) Transition to adult services and responsibility for their own health care takes place much earlier than it does for most young people, and for those in care it can happen very suddenly.(32) When they move to independent living care leavers (CLs) have to negotiate the transition from the familiar (place and people) to

the unfamiliar and, at age 18, from children's to adult services. The age at which young people have to move from children's services to adult services also comes 'at a time of marked risk to ongoing psychosocial development and wellbeing' (p.1(33)). Those with mental health needs are likely to find themselves without support at a time they need it most, and CLs are likely to face loneliness and isolation. In this arrangement of service provision, young people are faced with a system that is 'weakest where it needs to be strongest'.(34) Despite initiatives designed to improve the transition to adulthood, research reports that care leavers are often inadequately prepared for, or supported during, the multiple transitions entailed in leaving care.(35, 36) In their 2016 study(1) the Care Quality Commission cited one care leaver as saying:

'I don't know why the system thinks a 16-year-old is an adult. Kids in care haven't even had a childhood. How can we be an adult at 16?'

This study seeks to improve health outcomes for CLs by better equipping the staff responsible for them with appropriate knowledge and skills.(37)

1.3 Care Leavers' experiences of transition

Research with care leavers(38, 39) makes clear that the transition from care can, in and of itself, be highly stressful, as young people may be: living on their own, away from familiar environments, having suddenly to budget and care for themselves, and may be trying to re-connect with birth family members. A health survey completed by 418 care leavers found that 44% stated they regularly drank alcohol to excess and 29% had self-harmed.(40) Care leavers (CLs) felt that their health needs were not understood and they had found it difficult to access adult services. Many complained of misdiagnosis, a problem that other research has confirmed.(41) The most common theme reported in all studies of care leavers' views are feelings of isolation and loneliness.

Research into the subjective wellbeing of 474 care leavers, conducted at the University of Bristol in partnership with CORAM Voice, found that 22% said they had a disability or long term health condition affecting day to day activities; 20% were lonely 'all of the time', and 24% rated their anxiety as high (in comparison with17% of young people in the general population (see ONS 2017(42)). Care leavers commented:

'At 16, I was left to live in a half independent house miles from the school I attended and where my friends live. This left me isolated, unable to afford transport to see my friends. Which led to my relationships with my friends drifting apart.'

Leaving care for me was a bad experience at the start, had no support and was very vulnerable.'

1.4 Leaving care and the role of the Personal Advisor

In the Children and Social Work Act 2017, the Government introduced the requirement for local authorities (LAs) to publish a 'Care Leaver Offer', which outlines the services to support this transition for care leavers within the local authority area. LAs are mandated to provide a Personal Advisor (PA) to support CLs up to the age of 25 (at the time of the initial proposal only those CLs in education or training were eligible for support beyond age 21). The PA's role is to ensure a CL has the correct level of support and to coordinate and review the services needed to implement the CL's 'Pathway Plan', to take reasonable steps to ensure that the young person makes use of these, and to remain informed about their progress and wellbeing.(43) The Pathway Plan is required for all care leavers; it is designed to facilitate successful transition(44) and covers 8 eight areas of their lives, including their 'health and development' and 'emotional and behavioural development'. The Pathway Plan should include details of a young person's health needs and how these should be met, and the development of this plan should be supported by annual Health Assessments undertaken while in care. CLs themselves should be provided with a Health Passport when they leave care, summarizing their health history and needs for their own future reference.

The expectations of the PA is set out in the Children and Social Work Act 2017 and in the description of the 'named worker' in NICE guideline NG43.(45) NG43 covers a range of transitional situations, and those

deemed particularly relevant to the responsibilities of PAs are asterisked in the following extract from Sections 1.27 and 1.28.

'1.27 The named worker should:

- oversee, coordinate or deliver transition support, depending on the nature of their role;*
- be the link between the young person and the various practitioners involved in their support, including the named GP*
- arrange appointments with the GP where needed as part of transition*
- help the young person to navigate services, bearing in mind that many may be using a complex mix of care and support*
- support the young person's family, if appropriate
- ensure that young people who are also carers can access support
- act as a representative for the young person, if needed (that is to say, someone who can provide support or advocate for them)*

1.28 The named worker should ensure that the young person is offered support with the following aspect of transition if relevant for them (which may include directing them to other services)

- education and employment
- community inclusion*
- health and wellbeing, including emotional health*
- independent living and housing options.'

1.5 importance of improving the health and wellbeing of care leavers

Few data are routinely collected on the health and wellbeing of CLs, but evidence suggests that, compared with the general population of young adults, they fare less well.(25, 46-49) Most have poorer educational qualifications and socio-economic life chances,(50, 51) and poorer physical, emotional and mental health than comparable peers.(26, 37, 52-55) They are more likely than those who have not been in care to engage in risky behaviours, such as smoking, substance use and misuse, and unprotected sex. They are over-represented amongst the homeless,(56, 57) among young women who become teenage parents,(58) those who self-harm,(59, 60) and those involved with the criminal justice system.(57)

As well as the personal costs to young people, there are significant societal costs. For example, mothers who are CLs are at increased risk of parenting problems and unstable housing arrangements,(19, 61) and their children are more likely to be taken into care,(22) leading some women to avoid involvement with services.(62, 63) Using the costs to young people of not being in education, employment and training (NEET), the NAO estimated lifetime cost of the 2015 cohort of 19-year old care leavers to be around £240 million - £150 million more than if they had the same NEET rate as 19 year old young people who had not been in care.(64p7)

1.6 Why this research is needed now

LAs, Clinical Commissioning Groups and NHS England are required to ensure that effective plans are in place to enable children leaving care to continue to obtain the healthcare they need.(27) Research and guidance emphasise the importance of a named person who can develop a good relationship with a CL and ensure that s/he receives support and advice. For most CLs, the named person is the Personal Adviser (PA) who should be implementing their Pathway Plan, including supporting their health needs. By definition, most will meet the criteria for the 'named worker' in the relevant NICE Guideline (NG43, see previous). Statutory guidance(27) makes clear that PAs 'should have access to information and training about how to promote

physical and mental health' (p.26), to work in partnership with CLs and those health professionals involved in their health assessments, and to ensure that CLs have all the information they need to manage their own health. For those with complex needs, including disabilities, who do not meet the criteria for support by adult services, the PA should ensure that all possible forms of support are identified and made available.

Despite the statutory force of the guidance, health is rarely a major focus for PAs, who are primarily concerned with basic provision of housing and money.(65, 66) Whilst appropriate accommodation is essential for mental and physical health and wellbeing, many care leavers report that insufficient attention is given to their health needs, particularly their mental health needs and as the Care Quality Commission noted, most lack adequate health support.(1 p.36) This was confirmed in our discussions with care leavers whilst developing this proposal.

As adults with whom CLs have (ideally) already formed a supportive relationship, the PA is well placed to promote their health and wellbeing, and their use of health services. However, PA provision varies considerably across LAs,(58) and there is currently no prescribed professional qualification for PAs, other than to have a working knowledge of the issues a care leaver might face as they make their transition into adulthood, and the legal framework in relation to this. Little is known about in-service training provided by LAs, or the supervisory arrangements in place to support them in executing their role.

Without an explicit curriculum to equip PAs to address issues of health and wellbeing, it is unsurprising that these issues are seldom addressed. In preparing their transition Guideline(45) NICE was unable to identify any studies on the effectiveness of 'transition training' for practitioners responsible for supporting young people using children's health or social care services 'before, during and after transition' (2.9) The Care Leavers Association has recommended better training for PA, particularly in relation to mental health. This study will address this gap by developing a brief training intervention designed to equip PAs to better promote and facilitate the health and wellbeing of the care leavers.

2 AIMS AND OBJECTIVES

2.1 Aim

The study has two main aims, the first of which was to develop a training programme that will help PAs to identify and act on the health and wellbeing needs of care leavers. This has been completed. The second aim is to assess the feasibility of evaluating the effectiveness of the training programme in a definitive trial. The remainder of this protocol addresses this second aim.

2.2 Primary objective

To ascertain the feasibility of key procedural elements that would need to form part of an experimental evaluation of the effectiveness of the training intervention, including:

- Whether it is possible to recruit, train and retain all PAs in each participating authority.
- Whether it is possible to recruit and retain a sample of CLs in each arm of the study to a 12 month follow up.
- Whether it is possible to secure blinding of outcome assessors.

2.3 Secondary objectives

Secondary objectives are to:

- Establish the acceptability and feasibility (data burden and cost), and the factors influencing the completion of measures at baseline (PAs and CLs), post training (PAs) and follow up (PAs and CLs).
- To collect outcome measures and assess their performance and quality with this population (acceptability, completeness, means, variability and distribution of scores).
- To use the data collected to estimate the Intra-cluster Correlation Coefficient (ICC) to inform the sample size require for the main trial.
- Determine the feasibility + cost of accessing and using administrative data, if available
- Ascertain the acceptability to LAs and PAs of randomization
- Consider the implications of any contamination between the two arms of the trial e.g. PAs moving between teams in different trial groups.
- Identify barriers + facilitators to implementation of, and fidelity to, the intervention.
- To use the information gathered to inform the design of a pragmatic trial, if this seems feasible.

Outcome and outcome measures - Feasibility

Outcome 1: Recruitment of care leavers to the study

- Measurement: Count of care leavers randomised
- Timepoint: Feasibility study recruitment period for care leavers
- Outcome 2: Retention of care leavers
 - Measurement: Proportion of recruited care leavers who complete the study assessments
 - o Timepoints: 16, 32 and 48 post intervention
- Outcome 3: Blinded assessment
 - Measurement: Ask assessors to record whether the interviewee has an intervention or control PA - best guess if don't know (two-alternative forced choice).

- Timepoints: 16, 32 and 48 weeks post intervention
- Outcome 4: Recruitment of personal assistants
 - Measurement: Count of personal assistants recruited
 - o Timepoint: Feasibility study recruitment period for personal advisors
- Outcome 5: Fidelity to allocation
 - Measurement: Proportion of recruited personal advisors in intervention group who complete the training
 - o Timepoint: Feasibility study training period for personal advisors
- Outcome 6: Retention of personal advisors
 - Measurement: Proportion of recruited personal advisors who complete the study assessments
 - o Timepoints: post-training, 24 and 48 weeks

Intervention outcomes

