3.1 Project timetable

3.3 Planned recruitment rate

Personal Advisors

Participant personal advisors will be recruited from each of the participating local authorities. Whilst the local authority can require their staff to participate, and our aim is to recruit all PAs employed in the local authority, we intend to give personal advisors the option to withhold their consent to participate. In this feasibility study we are aiming to recruit from three groups of PAs at each of three local authorities.

Care Leavers

Participating care leavers will be recruited from each local authority until the target sample is reached (60 care leavers).

Recruitment will be proportionate to the size of the local authority and the flow of eligible care leavers and drawn equally from both arms of the study. We have not conducted a formal sample size calculation but are aiming to demonstrate the feasibility of a definitive RCT by recruiting around 20 care leavers at each of the three local authorities.

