6 TRIAL PROCEDURES

The study aims to recruit all Personal Advisors employed by the participating local authorities, and 60 Care Leavers, 30 from each arm of the trial. This section outlines the key trial procedures from identification of potential participants through to end of trial.

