6.6 Follow-up assessments

Follow-up assessments of Personal Advisors and Care Leavers will be conducted by members of the study team at 24 and 48 weeks following the completion of PA training. Wherever possible, peer researchers will be responsible for follow-up assessments with Care Leavers, supported by Coram Voice.

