6.7 Qualitative assessments

Care Leavers: At 24- and 48 weeks following the completion of training by PAs, we will collect qualitative data from our sample of care leavers on the extent to which they feel their health needs (including emotional health and wellbeing) have been recognized and addressed by their PAs in the previous six months. The interviews will explore how often they have seen their PA; whether PAs have brought up topics covered in training modules (including help seeking, smoking, alcohol and substance use, sexual health, nutrition and exercise); what their own health and wellbeing concerns are and whether or not they have felt able to bring these to the attention of their PA; what the response was, and how helpful their PA has been more generally in helping them to address their health issues. We will also enquire how the CL feels about health issues being raised by the PA, and whether or not they subsequently took any steps to address them.

At the 48 weeks interview we will also ask care leavers about their experiences of participating in the trial, and what their advice would be to a research team wanting to conduct a larger study. A particular focus of this conversation will be their views on the use of peer researchers, the incentives offered; what information they would want to know about the findings of the trial, and in what format.

All interviews with Care Leavers will be conducted via a conference facility or via Smartphone facility, unless and until circumstances change and face-to-face meetings are judged safe and appropriate.

Personal Advisors: At the 24- and 48- week follow up points we will re-interview the same PAs to explore:

- Frequency and content of contacts with CL, with particular focus on module topics;
- which modules have been most, and least, useful; how or why;
- what factors beyond the training have helped them to develop and implement a focus on health promotion activities with care leavers, and what factors have impeded this (factors to be explored

include organisational factors such as supervision, workload, follow-up support; personal factors such as lack of confidence, adverse experiences, and care leaver attributed factors such as lack of interest, refusal to discuss).

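### The only stated measure of assessor blinding is a forced choice that does not separate knowing the arm from guessing it, so modest unblinding cannot be excluded or explained

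*Protocol*

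**What the plan says.** Protocol section 2.2 lists three elements of the primary objective. The third is "Whether it is possible to secure blinding of outcome assessors". Section 2.3 defines the matching feasibility measure as Outcome 3: "Ask assessors to record whether the interviewee has an intervention or control PA - best guess if don't know (two-alternative forced choice". No item on knowledge, certainty or source of information is named.

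The number of records is bounded by the sample, given in section 6 as "60 Care Leavers, 30 from each arm of the trial". The number of rounds is stated in two ways. Outcome 3 gives "Timepoints: 16, 32 and 48 weeks post intervention", whereas section 6.6 places follow-up "at 24 and 48 weeks following the completion of PA training".

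On who assesses, section 6.6 says "Wherever possible, peer researchers will be responsible for follow-up assessments with Care Leavers, supported by Coram Voice". Section 6.11 says that peer researchers are not told the allocation. The follow-up interviews described in section 6.7 nevertheless ask care leavers "whether PAs have brought up topics covered in training modules".

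Section 10.1 states that no sample size calculation was done, and section 10.2 plans summary statistics only. Section 15 refers to progression criteria, but the protocol gives none for blinding.

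**The concern.** An assessor's knowledge has at least three states: was told or is sure, suspects, has no idea. Outcome 3 acknowledges that some assessors will not know, but asks them for the same two-way answer as those who do. As the outcome is defined, a disclosed allocation and a lucky guess give identical data. An analysis plan can choose how to summarise the answers, but it cannot restore a distinction that was never recorded.

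Disclosure is a realistic route here, because the interview itself covers the training content. A definitive trial would need to know how often the arm came out and by what route: a care leaver's remark, a slip by staff, or inference from the answers. The forced choice gives an imprecise answer to the first question and none to the second.

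**Working it through.** The protocol gives no power or precision figure for blinding, so there is none to reproduce. The checks below show what one round can tell.

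**Inputs.** Up to 60 records per round (sections 3.3 and 6). Assumptions, none from the protocol: records are independent; a share *u* of assessors know the arm and answer correctly; the rest guess at 50%; tests are exact, two-sided, at 5%.

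**1. What the pooled answer identifies.** The proportion correct is p = u + (1 − u)/2, so u = 2p − 1. Suppose 39 of 60 are correct (65%; exact 95% CI 51.6% to 76.9%). That fits nobody knowing and 39 of 60 lucky guesses. It equally fits 18 knowing plus 21 of 42 guesses correct (50%), since 18 + 21 = 39. The record cannot separate the two.

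**2. Precision of one round.** For 30 of 60 correct the exact 95% CI is 36.8% to 63.2%. The upper limit gives u = 2 × 0.632 − 1 = 0.264, so a perfect chance result is compatible with about 26% knowing. At u = 20% (p = 0.60) the half-width for u is 1.96 × 2 × √(0.60 × 0.40/60) = 0.248, about ±25 points.

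**3. Power of the forced choice against 50%.** With 60 records the critical value is 39 correct.

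| u | p correct | power |
|---|---|---|
| 10% | 55% | 8% |
| 20% | 60% | 26% |
| 30% | 65% | 56% |
| 40% | 70% | 84% |
| 50% | 75% | 97% |

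If retention were 80% or 70% (48 or 42 records), power at u = 20% would be 21% or 24%. The figures are not monotone because the test is discrete. Pooling two or three rounds of 60 gives 54% (120 records) or 75% (180) at u = 20%. Both are upper bounds, because the same care leavers and probably the same assessors recur. If each assessor did 20 interviews with an intra-assessor correlation of 0.05 to 0.10 (assumed), the design effect would be 1 + 19 × 0.05 = 1.95 to 1 + 19 × 0.10 = 2.90. That cuts 60 records to an effective 31 to 21.

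**4. What a certainty item adds.** Let *s* be the share of unblinded assessors who tick that they know, and *f* the share of blinded assessors who wrongly tick it, half of them correct by chance. Then P(know, correct) = us + (1 − u)f/2 and P(know, wrong) = (1 − u)f/2. Correct is compared with wrong among those who claim to know, by an exact sign test averaged over how many claim it. With 60 records and u = 20%:

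| s | f = 5% | f = 10% | f = 20% |
|---|---|---|---|
| 100% | 91% | 83% | 69% |
| 75% | 74% | 62% | 48% |
| 50% | 43% | 34% | 25% |
| 25% | 10% | 10% | 8% |

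The forced choice alone gives 26%. At s = 100% the half-width for u falls from ±25 to ±11–14 points. Recorded directly, 0 of 60 told or knowing has a 95% upper limit of 6.0%, and 12 of 60 gives 10.8% to 32.3%. At s = 50% the change in power is −1 to +17 points, and the difference P(know, correct) − P(know, wrong) = us centres on 10%, not the true 20%. At s = 25% the know-only measure does worse than the forced choice and centres on 5%.

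**The case against.** Two-alternative forced choice is an accepted format, and it denies assessors a don't-know option to hide behind. That stands, and it is the reason to keep it.

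The protocol recognises the difference between knowing and guessing, and the case report form, which is not shown, may record it. That is possible. But Outcome 3 fixes the response format and does not require such an item, so the protocol does not secure it.

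A feasibility study needs no power calculation, none is claimed, and no test against 50% is planned. This also stands: power serves here only as a gauge of information, and the small sample is not the defect. The interval for 30 of 60 correct makes the same point without any test.

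A reader might infer that about 60 interviews cannot show whether blinding held. The documents do not support that. Sixty is the count for one round, two or three rounds are planned, and even one round would probably reveal gross unblinding. Nor do they support saying that the trial would declare blinding feasible from a non-significant result: no such rule is stated, and no threshold for acceptable unblinding is given.

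The strongest objection is to the remedy. Allocation is not disclosed to peer researchers, so leakage would plausibly come from interview cues that produce suspicion, not certainty. A headline of knew-and-correct would then understate unblinding and could falsely reassure. This is right, and it limits the fix.

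**Conclusion.** The point holds as a cheap improvement to a measure that the protocol fixes, not as an error that invalidates the blinding outcome. The sole stated measure of a primary-objective element cannot distinguish knowledge from a correct guess and says nothing about how the arm was revealed. One round of 60 would probably detect 40% unblinding (about 84% power) but cannot exclude modest unblinding: a perfect chance result leaves up to about 26% possible.

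These figures assume independent records, full retention and guesses that are right half the time. Clustering by assessor or by group of Personal Advisors, or attrition, would generally weaken them. The benefit of a certainty item depends on the unknown share of unblinded assessors who would say that they know, so a large gain in precision is possible but not assured. Information on the source of unblinding would be new in any case.

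**What to change.** In Outcome 3, keep the forced choice and add one required item at each follow-up: *told or know / suspect / pure guess*, with the source recorded whenever the answer is not a pure guess. Report the following by arm and round, with 95% CIs:

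- the forced-choice percentage correct;
- the percentage correct within each certainty level;
- the proportion told or knowing.

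Knew-and-correct should not replace the forced-choice result, because assessors who only suspect would be missed.

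Reconcile the assessment times in Outcome 3 with those in section 6.6, because they determine how many rounds of blinding records there will be.

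The cost is one extra item on the assessor form and a sentence or two in section 2.3. Nothing now planned is lost. The downside is that self-rated certainty is subjective. The item must be in place before the first follow-up, because assessors' knowledge at interview cannot be reconstructed later.
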